6.3.3. Intervention Allocation to the Participant

Allocation of the participant to an intervention group at the study center will be performed using IVRS/IWRS through Interactive Response Tool (IRT) operated at the study level, before the first vaccination and after assessment of eligibility.

The actual randomization assignment that the participant received (to one of the groups) will be identifiable in IRT in case of unblinding.

After obtaining the signed and dated Informed Consent Form (ICF) (and informed assent form [IAF] if applicable) from the participant/participant's parent(s)/LAR(s) and having checked the eligibility of the participant, the delegated clinical study staff will access IVRS/IWRS. Upon entering the participant ID, the randomization system will determine the intervention group and provide the treatment number.

For all subsequent doses or replacement, new treatment numbers will be obtained through the IVRS/IWRS.

Refer to the IVRS/IWRS user guide or the SRM for specific instructions related to instances when IVRS/IWRS is not available.

Refer to the SRM for additional information related to the treatment number allocation.

6.3.4. Allocation of Participants to Assay Subsets

Immunogenicity assessments are planned as outlined in Section 8.1.

Refer to Section 9.3 for descriptions of analysis populations.

6.3.5. Blinding and Unblinding

6.3.5.1. Blinding

This study is observer-blind (double-blind for the 3 formulations of the investigational adjuvanted HPV vaccine and observer-blind for the investigational adjuvanted HPV vaccine versus *Gardasil 9*).

By observer-blind, it is meant that during the study, the vaccine recipient and those responsible for the evaluation of any study endpoint will be unaware of which vaccine was administered. To do so, vaccine preparation and administration will be done by a third party which will be a study center staff member who will not participate in any of the study clinical evaluation assays. The third party will know if the vaccine to dispense is the investigational adjuvanted HPV vaccine formulation or *Gardasil 9*. However, they will not know which one of the 3 investigational adjuvanted HPV vaccine formulations is dispensed (double-blind for the 3 formulations of the investigational adjuvanted HPV vaccine).

A blinded observer will participate in the participant's post injection assessments, perform clinical evaluations and record the clinical data.

The laboratory in charge of sample testing will be blinded to the study intervention assignment. Codes will be used to link the participant and study to each sample. There will be no link between the study intervention groups and the identity of the participant.

Unblinded monitors and in the event of a quality assurance audit, the auditor(s) will be allowed access to unblinded study intervention records at the site(s) to verify that randomization/dispensing has been done accurately.

6.3.5.2. Emergency Unblinding

Unblinding a participant's individual intervention number should occur ONLY in case of a medical emergency when knowledge of the intervention is essential for the clinical management or welfare of the participant.

In case of emergency, the investigator will have unrestricted, immediate, and direct access to the participant's individual study intervention through IVRS/IWRS. At activation, the study centers will be provided instructions and/or other applicable information for emergency unblinding in the SRM or other sources. The IRT used by the IVRS/IWRS provider will be programmed with blind-breaking instructions. In case of an emergency, the investigator has the sole responsibility for determining if unblinding of a participant's intervention is warranted. The participant's safety must always be the first consideration in making such a determination.

If a participant's intervention assignment is unblinded, the Medical Monitor (see the definition in Glossary of Terms) must be notified WITHIN 24 HOURS after breaking the blind. The date and reason that the blind was broken must be recorded in the source documentation (see the definition in Glossary of Terms) and eCRF, as applicable. The participant may continue in the study.

In the event of a Quality Assurance audit, the auditor(s) may be allowed access to unblinded study intervention information records to verify that vaccine dispensing has been done accurately.

A non-investigator physician (e.g., physician from emergency room) or participant/participant's parent(s)/LAR(s)/caregiver (see Glossary of Terms for a definition of a caregiver)/family member may also request emergency unblinding. Instructions for this will be provided to the participant/participant's parent(s)/LAR(s) at enrollment.

6.3.5.3. Emergency Unblinding Prior to Regulatory Reporting of Serious Adverse Events

GSK policy (which incorporates the International Council for Harmonisation [ICH] E2A guideline, European Union Clinical Study Directive, and the United States Federal Regulations) is to unblind the report of any unexpected serious adverse event (SAE) that is attributable/suspected to be attributable to the investigational vaccine prior to regulatory reporting.

IQVIA will follow these policies along with IQVIA's standard procedures and will be responsible for unblinding the intervention assignment in accordance with the specified time frames for expedited reporting of SAEs.

In addition, IQVIA may unblind the intervention assignment for any participant with a Suspected Unexpected Serious Adverse Reaction or an SAE that is fatal or life-threatening. If the SAE requires an expedited regulatory report be sent to 1 or more regulatory agencies, a copy of the report, identifying the participant's intervention assignment, may be sent to investigators in accordance with local regulations and/or GSK's policy.

6.4. Study Intervention Compliance

When participants are dosed at the site, they will receive the study intervention directly from the investigator or designee, under medical supervision. The date of administration of each study intervention dose will be recorded in the source documents.

6.5. Dose Modification

Not applicable.

6.6. Continued Access to Study Intervention After the End of Study

GSK will not be providing to the participants the continuing access to either study vaccine after the conclusion of the study.

6.7. Treatment of Overdose

Any dose of either study vaccine greater than the dose advised as per protocol is considered an overdose. All cases of vaccine overdose should be reported as adverse events (AEs) (or SAEs, if SAE criteria are met) and followed accordingly.

6.8. Concomitant Medications/Products and Concomitant Vaccinations

At each study visit/contact, the investigator or designee should question the participant or participant's parent(s)/LAR(s) about any medications/products taken and vaccinations received by the participant, whether prescribed or over the counter. Memory aids used by participant/participant's parent(s)/LAR(s) will be reviewed for any additional medication(s) and vaccination(s), which will be transcribed in eCRFs.

6.8.1. Recording of Concomitant Medications/Products and Concomitant Vaccinations

The following concomitant medication(s)/product(s)/vaccine(s) must be recorded in the eCRF:

- All concomitant medications/products, except vitamins and dietary supplements, administered during the 28-day period following each dose of study vaccine.
- Any concomitant vaccination administered in the period starting from the first dose of study vaccine and ending at the last study visit.
- All concomitant medication associated with AE, including vaccines/products, except vitamins and dietary supplements, administered after the first dose of study intervention.

- All concomitant medication leading to discontinuation of the study intervention or elimination from the analysis, including products/vaccines (refer to Section 5.2.2 and Section 9.3 for further details).
- Prophylactic medication (i.e., medication administered in the absence of ANY symptom and in anticipation of a reaction to the vaccination).
 - For example, an anti-pyretic is considered to be prophylactic when it is given in the absence of fever and any other symptom, to prevent fever from occurring
- Any concomitant medications/products/vaccines relevant to an SAE/potentially immune-mediated response (pIMD) to be reported as per protocol or administered during the study period for the treatment of an SAE/pIMD. In addition, concomitant medications relevant to SAEs and pIMD need to be recorded on the expedited AE report.

The Medical Monitor should be contacted if there are any questions regarding concomitant or prior therapy.

The record of a concomitant medication should include at a minimum the reason for use, dates of administration including start and end dates, dosage information including dose and frequency.

6.8.2. Concomitant Medications/Products/Vaccines That May Lead to Elimination of a Participant From Per Protocol Analyses

The use of the concomitant medications/products/vaccines listed in Section 5.2.2 will not require withdrawal of the participant from the study but may determine a participant's evaluability in the per protocol analysis. See Section 9.3 for cohorts to be analyzed.

6.9. Intercurrent Medical Conditions That May Lead to Elimination of a Participant From Per Protocol Analyses

At each study visit subsequent to the first vaccination, it must be verified if the participant has experienced or is experiencing any intercurrent medical condition (refer to Glossary of Terms for the definition of intercurrent medical condition). If it is the case, the condition(s) must be recorded in the AE section of the eCRF.

At the time of analysis, participants may be eliminated from the per protocol cohort for immunogenicity if, during the study, they incur a condition that has the capability of altering their immune response or are confirmed to have an alteration of their initial immune status.

7. DISCONTINUATION OF STUDY INTERVENTION AND PARTICIPANT DISCONTINUATION/WITHDRAWAL

7.1. Discontinuation of Study Intervention

Discontinuation of study intervention refers to any participant who has not received all planned doses of study intervention. A participant who discontinued study intervention may continue other study procedures (e.g., safety or immunogenicity), planned in this protocol at the discretion of the investigator.

The primary reason for premature discontinuation of the study intervention will be documented on the eCRF and may include (but not be limited to), the following:

- Adverse event requiring expedited reporting to IQVIA
- Pregnancy
- Unsolicited non-serious AE
- Solicited AE
- Not willing to be vaccinated
- Other (specify)

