2.3.3. Overall Benefit/Risk Conclusion

The investigational adjuvanted HPV vaccine is currently in an early stage of clinical development and no vaccine efficacy has been demonstrated in humans. Taking into account the measures to minimize the risk to the participants, the potential risks are justified by the potential benefits linked to the development of this investigational adjuvanted HPV vaccine.

3. Objectives and Endpoints

Table 4 Study Objectives and Endpoints

	Objectives	Endpoints
	Prin	nary
•	To evaluate the safety and reactogenicity of GlaxoSmithKline Biologicals SA (GSK)'s investigational adjuvanted human papillomavirus (HPV) vaccine formulations.	Percentage of participants reporting each solicited administration site event assessed as Grade 3 in terms of intensity within 7 days (Day 1 – Day 7) after each vaccine dose.
		 Percentage of participants reporting each solicited systemic event assessed as Grade 3 in terms of intensity within 7 days (Day 1 – Day 7) after each vaccine dose.
		Unsolicited adverse events (AEs)
		 Percentage of participants reporting unsolicited adverse event assessed as Grade 3 in terms of intensity classified by Medical Dictionary for Regulatory Activities (MedDRA) within 28 days (Day 1 – Day 28) after each vaccine dose.
		Serious adverse events (SAEs)
		 Percentage of participants reporting SAEs classified by MedDRA from first vaccination up to study end.
		Safety laboratory parameters (Step 1 participants)
		 Percentage of participants presenting clinically relevant abnormalities in each biochemical and hematological parameter at Day 7 post-dose 1.
•	To evaluate the immune response to GSK's investigational adjuvanted HPV vaccine formulations.	• Anti-HPV immunoglobulin G (IgG) antibody geometric mean concentrations (GMCs), 1 month after the third dose (Month 7).
	Secon	ndary
•	To evaluate the safety and reactogenicity of GSK's	Solicited events
	investigational adjuvanted HPV vaccine formulations.	 Percentage of participants reporting each solicited administration site event within 7 days (Day 1 – Day 7) after each vaccine dose.
		 Percentage of participants reporting each solicited systemic event within 7 days (Day 1 – Day 7) after each vaccine dose.
		Unsolicited AEs
		 Percentage of participants reporting unsolicited symptoms within 28 days (Day 1 – Day 28) after each vaccine dose.
		Potential immune-mediated disease (pIMDs)
		 Percentage of participants reporting pIMDs from first vaccination up to study end.

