7.2. Contraindications to Subsequent Study Intervention(s) Administration

The eligibility for subsequent study intervention administration must be confirmed before administering any additional dose.

All exclusion criteria have to be re-checked to ensure that the participant is still eligible. In addition, participants who meet any of the criteria listed below should not receive additional dose of study intervention.

- Study participants who experience any SAE judged to be possibly or probably related to study intervention or non-study concomitant vaccine/product, including hypersensitivity reactions.
- Study participants who develop any new condition which, in the opinion of the investigator, may pose additional risk to the participant if she continues to participate in the study.
- Anaphylaxis following the administration of study intervention.
- Any condition that in the judgment of the investigator would make intramuscular injection unsafe.
- Occurrence of a new pIMD (see Table 21 for the list of pIMDs) or the exacerbation of an existing pIMD that, in the opinion of the investigator, expose the participant to unacceptable risk from subsequent vaccination. In such cases, the investigator should use his/her clinical judgment prior to administering the next dose of study intervention.

The participants who have become ineligible for subsequent study intervention administration should be encouraged to continue other study procedures, at the investigators' discretion. All

relevant criteria for discontinuation of study intervention administration must be recorded in the eCRF.

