7.3. Participant Discontinuation/Withdrawal From the Study

A participant is considered to have withdrawn from the study if no new study procedure has been performed or no new information has been collected for her since the date of withdrawal/last contact.

From an analysis perspective, a study "withdrawal" refers to any participant who did not return for the concluding visit.

Investigators will attempt to contact participants who do not return for scheduled visits or follow-up.

All data and samples collected up to and including the date of withdrawal of/last contact with the participant will be included in the study analyses.

The primary reason for study withdrawal will be documented in the eCRF based on the list below:

- AEs requiring expedited reporting to IQVIA
- Unsolicited non-serious AEs
- Solicited AE
- Withdrawal by participant, not due to an AE*
- Migrated/moved from the study area
- Lost to follow-up
- Sponsor study termination
- Other (specify)

*If a participant is withdrawn from the study because she withdrew consent and the reason for withdrawal was provided, the investigator must document this reason in the eCRF.

Participants who are withdrawn from the study because of AEs/SAEs must be clearly distinguished from participants who are withdrawn for other reasons. Investigator will follow participants who are withdrawn from the study due to an AE/SAE until the event is resolved.

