8.3.4. Follow-up of AEs and SAEs, Pregnancies, and pIMDs

After the initial AE/SAE/pIMD, or pregnancy report, the investigator is required to proactively follow each participant at subsequent visits/contacts. All SAEs and pIMDs will be followed until resolution, stabilization, the event is otherwise explained, or the participant is lost to follow-up.

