- Implantable progestogen-only hormonal contraception associated with inhibition of ovulation
- Intrauterine device
- Intrauterine hormone-releasing system
- Bilateral tubal occlusion

Vasectomized partner

A vasectomized partner is a highly effective contraception method provided that the partner is the sole male sexual partner of the female participant of childbearing potential and the absence of sperm has been confirmed. If not, an additional highly effective method of contraception should be used.

Male partner sterilization prior to the female participant's entry into the study, and this male is the sole partner for that participant,

The information on the male sterility can come from the site personnel's review of the participant's medical records; medical examination and/or semen analysis, or medical history interview provided by her or her partner.

Sexual abstinence

Sexual abstinence is considered a highly effective method only if defined as refraining from heterosexual intercourse during the entire period of risk associated with the study drug. The reliability of sexual abstinence needs to be evaluated in relation to the duration of the study and the preferred and usual lifestyle of the participant.

Female Participants who Become Pregnant

Refer to Section 8.3 and Appendix 4 for the information on detection, recording, reporting and follow-up of pregnancies.

Any female participant who becomes pregnant during the study will need to discontinue further vaccination but may continue other study procedures at the discretion of the investigator.

^{*}Typical use failure rates may differ from those when used consistently and correctly. Use should be consistent with local regulations regarding the use of contraceptive methods for participants in clinical studies.

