3.3. Tertiary Objectives

3.4. Estimands

The primary and secondary estimands to support regulatory decisions are described in the following table:

Document: \\quintiles.net\Enterprise\Apps\sasdata\SAS\\SAS\GlaxoSmithKline\HPV\213749

(HPV9)\Biostatistics\Documentation\SAP\GSK 213749(HPV9-AS04-

001)_WZA97329_SAP_Final_v3.0_02FEB2024.docx

Author: PPD Version Number: 3.0

Version Date: 02FEB2024

Template No.: CS_TP_BS016 Revision 7 Reference: CS_WI_BS005

Effective Date: 01Nov2021

Page 12 of 48

Table A: Objectives and Estimands

Estimand	mand Attributes					
	Treatment	Population	Variable (or	Intercurr	ent events (ICEs)	Population level summary
			endpoint)	Description	Handling strategy	
Primary	Randomized HPV dose (High, Medium or Low) or Gardasil 9	Female participants between 16 and 26 years old	Each grade 3 solicited administration site event within 7 days after each vaccine dose	1. eDiary not completed on each day	1. Missing data won't be imputed. All data collected will be included in the summaries (treatment policy).	Percentage of participants with event with exact 95% Confidence Interval (CI)
Primary	Randomized HPV dose (High, Medium or Low) or Gardasil 9	Female participants between 16 and 26 years old	Each grade 3 solicited systemic event within 7 days after each vaccine dose	1. eDiary not completed on each day	1. Missing data won't be imputed. All data collected will be included in the summaries (treatment policy).	Percentage of participants with event with exact 95% CI
Primary	Randomized HPV dose (High, Medium or Low) or Gardasil 9	Female participants between 16 and 26 years old	Each grade 3 unsolicited adverse event within 28 days after each vaccine dose	1. Permanently discontinuation from study treatment due to any reasons	1. Missing data won't be imputed. All data collected will be included in the summaries (treatment policy).	Percentage of participants with event with exact 95% CI
Primary	Randomized HPV dose (High, Medium or Low) or Gardasil 9	Female participants between 16 and 26 years old	Serious Adverse Events from first vaccination up to study end	1. Permanently discontinuation from study treatment due to any reasons	1. Missing data won't be imputed. All data collected will be included in the summaries (treatment policy).	Percentage of participants with event with exact 95% CI

Document: \quintiles.net\Enterprise\Apps\sasdata\SASb\SAS\GlaxoSmithKline\HPV\213749

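### Surveillance for new SAEs and pIMDs is left to the investigator's discretion once dosing stops, which conflicts with endpoints to study end, the SAP's treatment-policy handling and Section 8.3.4

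*Protocol*

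**What the plan says.** **After dosing stops.** Protocol Section 7.1 states that a participant who has stopped study intervention "may continue other study procedures (e.g., safety or immunogenicity), planned in this protocol at the discretion of the investigator". Safety procedures are thus named as optional. Section 7.2, on women who become ineligible for further doses, is warmer but keeps the discretion: they "should be encouraged to continue other study procedures, at the investigators' discretion". Appendix 5 says that a participant who becomes pregnant "will need to discontinue further vaccination but may continue other study procedures at the discretion of the investigator", and Appendix 4 repeats this.

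**Endpoints and analysis.** Protocol Section 3, Table 4 defines the primary SAE endpoint as "Percentage of participants reporting SAEs classified by MedDRA from first vaccination up to study end". The secondary pIMD endpoint covers the same period. SAP Table A lists permanent discontinuation of study treatment as the intercurrent event for both. It handles the event by treatment policy, summarising what was collected and imputing nothing. SAP table shells 14.3.1.7 (SAEs) and 14.3.2.8.1 (pIMDs) use the whole Exposed Set as denominator, with no allowance for time under observation.

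**Mandatory follow-up.** Section 8.3.4 obliges the investigator, after a first AE, SAE, pIMD or pregnancy report, to follow the participant proactively at later visits or contacts. It adds: "All SAEs and pIMDs will be followed until resolution, stabilization, the event is otherwise explained, or the participant is lost to follow-up". Appendix 4 repeats both duties. Section 7.3 states: "Investigator will follow participants who are withdrawn from the study due to an AE/SAE until the event is resolved". Appendix 4 also has pregnancies followed to outcome, and any outcome that is an SAE reported as one.

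**The concern.** A treatment-policy strategy counts events whether or not dosing continued, so it needs data after discontinuation. The protocol does not require those data to be sought. Because the denominator is every vaccinated woman, time that nobody observed is treated as free of events. If investigators choose which women stay under surveillance, the missing data may also be related to risk.

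This matters more than usual here. Section 8.2.3.1 describes a first administration in humans. Section 2.3.1, Table 3 relies on collecting pIMDs for the whole study as part of the mitigation of the theoretical autoimmune risk. A woman who stops dosing also loses some of the protection of being asked about new events.

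**Working it through.** **1. The plan's own safety figures.** Section 9.2.1 gives a probability of at least 93% of seeing one or more Grade 3 AEs in 270 women at a true rate of 1.0%. Check: 1 − 0.99^270 = 0.934, which agrees. Exact limits reproduce Table 17, including upper limits of 1.4% for 0 of 270 and 2.0% for 1 of 270. The documents give no figure for follow-up after dosing stops.

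**2. Who is exposed.** Sections 9.4.1.1 and 9.4.2.1 make a woman a case on her first report of an SAE or a pIMD.

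| Stopped for | SAE endpoint | pIMD endpoint |
|---|---|---|
| SAE | already a case | later pIMD can be missed |
| non-serious pIMD | later SAE can be missed | already a case |
| pregnancy | outcome followed; other SAEs can be missed | can be missed |
| non-serious AE or solicited event | can be missed | can be missed |
| no reportable event (e.g. not willing to be vaccinated) | can be missed | can be missed |

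In the last row the duty in Section 8.3.4 is never triggered. In the other rows it is triggered, but it operates at later visits or contacts, which Sections 7.1 and 7.2 and the appendices leave optional. Section 8.3.1 adds that once participation has ended the investigator has no duty to look for new AEs or SAEs.

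For women who are already cases, a second and different event would not change the overall percentage. It would change the SOC and preferred-term rows and the event counts in the same shells.

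**3. Observation time at risk** (planned intervals, Protocol Table 2: Visit 3 at day 60, Visit 5 at day 180, Visit 7 at day 360), if she leaves at the visit where dosing stops:
- Visit 3: (360 − 60)/360 = 300/360 = 83%.
- Visit 5: (360 − 180)/360 = 180/360 = 50%.

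**4. One missed event.** 1/270 = 0.37 percentage points. Between 0 and 1 observed events, the upper limit in Table 17 moves from 1.4% to 2.0%.

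**5. Illustration on assumed values.** Assume a true 12-month rate p = 1%, events uniform over time, and a share d of women not yet cases who stop and leave with L = 10/12 of the period unobserved. The observed rate is p(1 − dL). If leavers have R times the later risk, the true rate is p(1 − dL) + d·R·p·L.

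| d | Observed rate | P(at least 1 event), R = 1 | Relative understatement, R = 1 | Relative understatement, R = 3 |
|---|---|---|---|---|
| 2% | 0.98% | 93.1% | 1.7% | 4.8% |
| 5% | 0.96% | 92.6% | 4.2% | 11.5% |
| 10% | 0.92% | 91.7% | 8.3% | 21.4% |

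With no loss, P(at least 1 event) is 93.4%. Expected missed events per group at R = 3 are 270·d·R·p·L. For d = 5% that is 270 × 0.05 × 3 × 0.01 × 10/12 = 0.34, and for d = 10% it is 0.68.

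**The case against.** A reader might infer that women stopped for a related SAE, a pIMD or pregnancy drop out of follow-up and count as event-free. The documents do not support that. The event that stops dosing is itself a case in its own endpoint. Pregnancies are followed to outcome, and an outcome that is an SAE must be reported.

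Nor do all women who stop lack required contact. Section 8.3.4 and Appendix 4 require proactive follow-up of the participant, not only of the event. The Schedule of Activities records SAEs, pIMDs and pregnancies at every visit to Month 12. Section 7.3 requires attempts to reach women who miss visits. Section 7.2 says that ineligible women "should be encouraged to continue other study procedures". Participants are also told to contact the investigator about signs they perceive as serious.

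The analysis is descriptive, the all-vaccinated denominator is openly stated, and the SAP tabulates disposition and attendance by visit, so gaps would show. A further amendment needs ethics approval, possibly re-consent, and would come after many early stops.

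Most of this stands and narrows the point. It does not remove it. A proactive duty exercised at visits that another section makes optional is a contradiction, and it never arises for a woman who stops without a reportable event. Attendance tables show that follow-up was cut short, not whether an event was missed.

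**Conclusion.** The point holds in limited form. The protocol lets surveillance for new SAEs and pIMDs lapse after dosing stops. That is inconsistent with its own endpoint period, with the SAP's treatment-policy handling and with Section 8.3.4. The exposure is confined to women not yet cases in the endpoint concerned, plus the SOC, preferred-term and event-count rows for women who already are.

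The size cannot be derived from the documents, which give neither a stopping rate nor the share who would leave. It is probably modest. On the assumed values above, fewer than one event per group is missed even at 10% leaving with tripled risk, and at equal risk the chance of seeing an event hardly moves. The relative understatement becomes noticeable only if leavers are both numerous and at higher risk. The reason to act is consistency and participant safety more than a demonstrated large bias. It is a worthwhile correction, not a threat to the trial's conclusions.

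**What to change.** Reconcile Sections 7.1 and 7.2 and Appendices 4 and 5 with Section 8.3.4, Table 4 and SAP Table A. State that every vaccinated woman who stops dosing continues SAE, pIMD and pregnancy data collection to Month 12 unless she withdraws consent. Collection can be at the scheduled visits or by phone. Section 8.4 allows phone contact only in special circumstances, so that route would have to be extended. Keep investigator discretion only for the immunogenicity blood draws. No dosing or stopping rule changes.

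The visits and recording already exist. The cost is amendment wording with its ethics review, re-consent if the consent form changes, and a few more contacts per site. Women who left before the change would not be recovered.
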